4.4 STUDY RESTRICTIONS

The following restrictions should be applied during the study and should be checked at the clinical unit at each visit, from the start of the screening visit and until the end of the last treatment period (i.e. when the subject leaves the clinic on Day 8 of TP2):

- No smoking or intake of substances containing nicotine, and no use of any kind of smoking electronic device (e.g. e cigarettes): during the entire study period (excluding the follow-up).

Clinical Study Code No.: CLI-05993AB6-06

Version No.: 1.0

Date: 16 February 2023

EudraCT number: 2022-003247-97

The following restriction should be applied before the screening visit:

- No strenuous activities: within 24 hours before the start of the screening visit and until the end of the visit.

The following restrictions should be applied prior to each visit with spirometry assessments (i.e. screening visit and Day 1 and Day 8 of both TP1 and TP2) and before each visit with MCC assessments (i.e. Day -1 and Day 8 of both TP1 and TP2):

- No intake of intoxicants such as alcohol, caffeine/xanthine containing beverages or food (coffee, tea, chocolate, cola) within 8 hours. Decaffeinated products are permitted;
- No strenuous activities within 1 hour;
- Avoiding wearing clothes that substantially restrict full chest and abdominal expansion.

The following restriction should be applied prior to each visit with blood collection for laboratory tests (i.e. the screening visit and Day 8 of TP2, or the early termination visit [if applicable]):

- No food intake: within 10 hours before the blood collection.

If these restrictions are not respected, the visit can be rescheduled once and all the information regarding the restriction(s) that are not respected will be recorded in the electronic case report form (eCRF). If the restriction(s) are again not respected at the rescheduled visit, the visit will be performed anyway and all the information regarding the restriction(s) that are not respected will be recorded in the eCRF.

4.5 DISCONTINUATION FROM STUDY

Subjects must be discontinued from the study for any of the following reasons:

- An AE occurs that, in the opinion of the Investigator, makes it unsafe for the subject to continue in the study. In this case, the appropriate measures will be taken;
- The subject is lost to follow-up;
- The subject withdraws consent;
- The subject's safety is affected by a violation of inclusion or exclusion criteria;
- The subject's safety is affected by the use of a non-permitted concomitant medication;
- The subject, in the opinion of the Investigator, is unwilling or unable to adhere to the study requirements (i.e. non-compliance);
- The Sponsor, the regulatory authorities, or the Ethics Committee(s) (EC[s]), for any reason, terminates the entire study or for this particular subject;
- The subject becomes pregnant.

It is understood by all concerned that an excessive rate of discontinuations can render a study uninterpretable; therefore, unnecessary discontinuations of subjects should be avoided.

However, should a subject discontinue the study, all efforts will be made to complete and report the observations as thoroughly as possible.

If a subject withdraws consent and cannot or is unwilling to attend the early termination visit, this visit will not be carried-out and no data will be collected after withdrawal.

If the subject has not withdrawn his/her consent, an early termination visit should be scheduled to perform the following safety assessments, as described in [Table 2](#) and [Section 7.1.3](#):

- Physical examination;

Clinical Study Code No.: CLI-05993AB6-06

Version No.: 1.0

Date: 16 February 2023

EudraCT number: 2022-003247-97

- ECG (HR, QRS, PR and QTcF) and vital signs (DBP, SBP and oxygen saturation levels [SpO₂]);
- Recording of AEs, concomitant medications and study restrictions;
- Safety blood assessments (clinical chemistry, haematology, fasting glucose);
- Urine pregnancy test.

If the early termination visit is performed less than 7 days after the intake of the last dose of study treatment, a follow-up call (or visit, if deemed necessary by the Investigator) will also be performed 7 to 10 days after the last dose of study treatment.

In case of discontinuation from the study, the Investigator must fill-in the “Study Termination” page of the eCRF, reporting the main reason for withdrawal.

The subject number assigned to an individual who is withdrawn or who drops out of the study will not be reassigned to another subject.

4.6 SCREEN FAILURES

Screen failures are defined as potential participants who sign the ICF but are not subsequently randomised or entered in the study.

Subjects who do not meet the criteria for participation in the study (screen failures) may be rescreened once: the re-screening is allowed if the impacted criterion-in the Investigator’s opinion-linked to a temporary condition. Rescreened participants should be assigned a new participant number for the rescreening event.

5. CONCOMITANT MEDICATIONS

5.1 PERMITTED CONCOMITANT MEDICATIONS

1. Occasional paracetamol (maximum 2 g per day, with a maximum of 10 g per 14 days, for mild non-excluding conditions [see exclusion criterion #2, [Section 4.3](#)]);
2. Hormonal contraceptives;
3. Hormonal replacement treatment for post-menopausal women;
4. COVID-19 vaccine during the wash-out periods and at least 7 days before Day 1 of each treatment period.

Note: Any systemic symptoms (e.g. myalgia, fever, chills, fatigue) after COVID-19 vaccine should subside 2 days before the next treatment period. Otherwise, wash-out period extension should be evaluated on a case-by-case basis.

5.2 NON-PERMITTED CONCOMITANT MEDICATIONS

1. From 3 months before screening and up-to the end of the follow-up period: any enzyme-inducing drugs, enzyme-inhibiting drugs, biologic drugs or any drug known to have a well-defined potential for hepatotoxicity (e.g. isoniazide, nimesulide, ketoconazole);
2. From 3 weeks before randomisation and up-to the end of the follow-up period: any drug treatment, including prescribed or over-the-counter medicines, vitamins, herbal medicines, homeopathic remedies, etc., with the exception of the allowed concomitant medications specified above.

Clinical Study Code No.: CLI-05993AB6-06

Version No.: 1.0

Date: 16 February 2023

EudraCT number: 2022-003247-97

The wash-out requirements prior to the assessments of MCC and lung function are summarised in [Section 4.4](#).

6. TREATMENTS

The study treatments will be supplied to the investigational centre under the responsibility of the Sponsor, who will also provide the Pharmacist/Investigator with appropriate certificates of analytical conformity.

6.1 TREATMENTS BEING INVESTIGATED

6.1.1 APPEARANCE AND CONTENT

Test treatment: placebo HFA-152a propellant pMDI, presented as:

- Active ingredients: none;
- Excipients: HFA-152a propellant, [REDACTED];
- Presentation: each canister contains 120 doses;
- Appearance: aluminium canister + grey actuator.

Reference treatment and training kit: placebo HFA-134a propellant pMDI*, presented as:

- Active ingredients: none;
- Excipients: HFA-134a propellant, [REDACTED];
- Presentation: each canister contains 120 doses;
- Appearance: aluminium canister + grey actuator.

*For this study, CHF 1535 placebo HFA-134a propellant pMDI will be used.

6.1.2 DOSAGE AND ADMINISTRATION

6.1.2.1 RATIONALE FOR DOSE SELECTION

The dose of test treatment and reference treatment administered in this study (i.e. 5 inhalations BID for 8 days) corresponds to the maximum total daily dose of HFA-134a propellant allowed for administration with the Clenil pMDI device, according to the current SmPC (for Clenil 100 µg, the maximum allowed daily dose is 1000 µg, administered as 500 µg BID).

6.1.2.2 DOSAGE

Subjects will receive 5 inhalations BID (morning and evening), for a total of 8 days, of each of the following treatments:

- **Test treatment:** placebo HFA-152a propellant pMDI;
- **Reference treatment:** placebo HFA-134a propellant pMDI.

The administration of the study treatment will occur using two pMDI canisters and two actuators (one for each of the two treatment periods) for each subject.

Investigational Phase

At Day 1 of each treatment period, each subject will receive a treatment box containing 2 pMDI devices: one device with a canister identified with a green sticker on the top, and one device with a

Clinical Study Code No.: CLI-05993AB6-06

Version No.: 1.0

Date: 16 February 2023

EudraCT number: 2022-003247-97

canister identified with a red sticker on the top. Subjects will be advised to use the device with a canister identified with a green sticker. The device with a canister identified with a red sticker should be used only if the one with a green sticker does not function normally.

According to the allocation based on the randomisation list, eligible subjects will be administered multiple doses (5 inhalations BID, for a total of 8 days) of each of the following study treatments in a cross-over design:

- **Test treatment:** placebo HFA-152a propellant via pMDI;
- **Reference treatment:** placebo HFA-134a propellant via pMDI.

The first dose (morning of Day 1) and the last dose (morning of Day 8) of each treatment will be administered at the investigational centre.

From the evening of Day 1 to the evening of Day 7 of each treatment period, subjects will continue the study treatment administration at home. They will use a DRC to record compliance to the study treatment, the use of concomitant medications and the occurrence of AEs (see [Section 7.2.7](#)).

6.1.2.3 ADMINISTRATION

The study treatment will be administered by inhalation, using the pMDI device with a canister identified with a green sticker (in case of dysfunction, the pMDI with a canister identified with a red sticker should be used). The instructions to be followed during the administration of the study treatments will be provided in a separate document.

Subjects will be advised not to take the study treatment in the morning of Day 8 of each treatment period.

Treatment administration will be recorded in the eCRF by the Investigator or designee. Any issues occurring during the inhalations as evaluated by the Investigator or designee will be reported in the eCRF.

6.1.2.4 SUBJECT TRAINING

6.1.2.4.1 Training with AIM™ Vitalograph®

At screening, the AIM™ Vitalograph® will be used to train the subjects to use the pMDI inhaler correctly. Inhalation through a specific placebo inhaler (different from the one described in [Section 6.1.2.4.2](#)) at the normal range (corresponding to a required peak inhaled flow rate of 30 L/min) will be recorded and evaluated by the AIM™ device, due to its ability to monitor the correct timing of the actuation, proper inhalation time, proper flow and breath holding. Once three consecutive successful inhalations are detected by the AIM™ device, the subjects will be told to continue using the same inspiratory flow rate while inhaling the study treatment. Detailed instructions for use of the AIM™ device are reported inside the commercial package.

Subjects will not be included in the study if the training is not completed successfully. Training evidence will be recorded in the eCRF, including the three AIM™ device results.

6.1.2.4.2 Training with Pressurised Metered Dose Inhaler Placebo

At screening, the correct use of the pMDI device will be explained to the subjects according to the instructions for use (provided in a separate document).

Subjects will be trained by using a placebo HFA-134a inhaler, which is identical from a functional point of view to the device used for the administration of the study treatments (see [Section 6.3.2](#)). Therefore, the training will be done with the pMDI device, with the inhalation repeated five times or as many times as necessary until the subject is properly trained.

Clinical Study Code No.: CLI-05993AB6-06

Version No.: 1.0

Date: 16 February 2023

EudraCT number: 2022-003247-97

The training kits will be kept at the investigational centre by the Investigator and will not be dispensed to the subjects. The training kit will be assigned to the subject at screening.

The subject will not be included in the study if the training is not completed successfully. Training evidence will be recorded in the eCRF by the Investigator or designee.

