12.3.5 SAFETY VARIABLES

Adverse Events

All AEs starting on or after the time of first study drug intake will be classified as treatment-emergent adverse events (TEAEs). Any AEs started after the informed consent signature and before the time of first study drug intake will be classified as pre-treatment AEs.

The number of TEAEs and the number and percentage of subjects who experienced at least one TEAE will be presented for each study treatment for all AEs, ADRs, SAEs, non-serious AEs, serious ADRs, severe AEs, AEs leading to study discontinuation, and AEs leading to death. Summaries will be presented overall and by system organ class (SOC) and preferred term (PT) based on the MedDRA dictionary.

All AEs will be listed. Pre-treatment AEs will be listed only.

ECG

At baseline and at each post-dose timepoint, the following statistics will be presented for each study treatment for the ECG parameters (HR, QRS, PR, QTcF):

- Mean absolute value with its 95% CI;
- Mean change from baseline with its 90% CI (for post-dose time-points only).

For QTcF, the following categories will also be analysed for each study treatment, by means of descriptive statistics:

- For male subjects: QTcF interval > 450 ms, > 480 ms and > 500 ms;
- For female subjects: QTcF interval > 470 ms and > 500 ms;

Clinical Study Code No.: CLI-05993AB6-06

Version No.: 1.0

Date: 16 February 2023

EudraCT number: 2022-003247-97

- For both, male and female subjects: change from baseline > 30 ms and > 60 ms.

The analysis will be presented at each post-dose timepoint and at any post-dose timepoint.

Vital Signs

At baseline and each post-dose timepoint, the following statistics will be presented by treatment for the vital signs parameters (SBP, DBP, SpO₂):

- Mean absolute value with its 95% CI;
- Mean change from baseline with its 95% CI (for post-dose time-points only).

Lung function parameters

Descriptive statistics on actual values and change from baseline will be presented for FEV₁ and FVC. Both absolute and relative changes from baseline will be presented.

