### **3.1.3 Presentation of results**

Tables will present TEAEs only. Pre-treatment AEs will only be listed.

An overview table will show the number and percentage of subjects with at least one event and the number of events by treatment and overall for the following:

- TEAEs
- Serious TEAEs
- Non-serious TEAEs
- ADRs
- Serious ADRs
- Severe TEAEs
- TEAEs leading to study drug discontinuation
- TEAEs leading to death

Separate summary tables by MedDRA system organ class and preferred term will show the number and percentage of subjects with at least one event and the number of events by treatment and overall for the aforementioned categories. Each AE record in the clinical database is considered as a distinct adverse event and is counted as such. Blank system organ classes and preferred terms, if any, will be shown as ‘Not Available’ in the tables and listings.

All AEs, including pre-treatment events and all coding information will be listed. AEs started on or after the date of the follow-up call/visit will be flagged as ‘Follow-

	Statistical Analysis Plan	
CLI-05993AB6-06	Final Analysis	Final 1.0 of 05OCT2023

up'. COVID-19 related AEs will be flagged. Separate listings will be prepared for the categories presented in the summary tables.

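### A reaction at the first in-study exposure to HFA-134a, taken as training at screening, cannot enter the TEAE or ADR tables, whereas one at the first exposure to HFA-152a does

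*Protocol*

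**What the plan says.** Protocol 6.1.1 describes one product for two uses: "Reference treatment and training kit: placebo HFA-134a propellant pMDI". Protocol 6.1.2.4.2 confirms this: "Subjects will be trained by using a placebo HFA-134a inhaler". The number of training inhalations is open-ended: "the training will be done with the pMDI device, with the inhalation repeated five times or as many times as necessary". Training is a condition of entry: "The subject will not be included in the study if the training is not completed successfully". Protocol 6.3.2 restricts the training kits to screening, and no training with HFA-152a is described anywhere.

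On adverse events, Protocol 12.3.5 says that those starting after consent and "before the time of first study drug intake will be classified as pre-treatment AEs". SAP 3.1.2 starts the TEAE window at the first administration of study treatment and defines ADRs as a subset of TEAEs. SAP 5.2.1 ends the Screening phase one minute before the first administration in the first available period. SAP 3.1.3 then says: "Tables will present TEAEs only. Pre-treatment AEs will only be listed". The listing is 16.2.7.1, on the Randomised Set.

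Protocol 11 says that screening failures are not entered in the eCRF. Protocol 7.1.1 and 10.8 have adverse events recorded there from consent onwards.

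**The concern.** The secondary objective is to evaluate the safety and tolerability of both propellants, and the main output for it is a set of TEAE and ADR tables by treatment. Readers will look across the two columns. For that reading to be fair, the first exposure to each propellant should be handled in the same way.

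Here it is not. The first inhalation of HFA-152a always falls inside the counted window, and the first in-study inhalation of HFA-134a always falls outside it. Crossing over does not balance this, because the training comes before both sequences. A subject who coughs at first use of a propellant, and not again, would be tabulated for HFA-152a and not for HFA-134a. If that subject is then screened out, the HFA-134a event is missing from the listing as well. Neither document mentions the training exposure in the safety analysis.

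**Working it through.** The plan gives no figure for this point, so there is none to reproduce. The check has three parts.

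**1. Amount and timing of the training exposure**

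- One study dose is 5 inhalations (Protocol 6.1.2.2). Training is 5 inhalations or as many as are needed, so about one full dose or more. The text does not call five a minimum, but that is its natural reading.
- Scheduled inhalations per completed period (SAP 4.6.2): 5 × (2 × 8 − 1) = 75, or 75 / 5 = 15 doses. Five training inhalations are 5 / 75 = 6.7% of a period's exposure.
- Screening is 2 to 21 days before Day -1 (Protocol 7.1.1), and Day 1 is the day after Day -1 (Protocol 7.1.2.1.2). The gap from training to first dose is therefore 2 + 1 = 3 to 21 + 1 = 22 days.

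**2. Where each exposure falls under SAP 5.2.1**

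| Exposure | When | Phase | Adverse event output |
|---|---|---|---|
| First in-study HFA-134a (training) | Screening | Screening | Listing 16.2.7.1 only |
| First randomised HFA-134a dose | Day 1 of its period | Treatment | TEAE tables (a re-exposure) |
| First HFA-152a dose | Day 1 of its period | Treatment | TEAE tables |

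If all subjects reach both periods, first in-study exposure is in the tabulated window for 20 of 20 subjects on HFA-152a and 0 of 20 on HFA-134a, in both sequences.

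There are two edge cases. Under SAP 3.1.2 an event whose incomplete start date leaves the phase open goes to the treatment phase. A delayed event that starts after the first randomised dose becomes a TEAE of the Period 1 propellant.

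**3. Illustration of size**

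The following are assumptions, not document figures:

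- N = 20, and all subjects are randomised and reach both periods.
- The same probability p applies to a reaction at first exposure to each propellant.
- Reactions are specific to the propellant, so earlier use of one does not change the reaction to the other.
- A subject who reacts at training reacts again during the HFA-134a period with probability r, and no other subject reacts to HFA-134a.

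Expected subjects tabulated are N·p on HFA-152a and N·p·r on HFA-134a, so the spurious difference is N·p·(1 − r). With p = 0.10:

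| r | HFA-152a | HFA-134a | Difference |
|---|---|---|---|
| 0 | 20 × 0.10 = 2.0 | 0 | 2.0 |
| 0.25 | 2.0 | 0.5 | 1.5 |
| 0.50 | 2.0 | 1.0 | 1.0 |
| 1.00 | 2.0 | 2.0 | 0 |

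All counts are proportional to p: they halve at p = 0.05 and double at p = 0.20. The true difference is zero in every row.

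**The case against.** The strongest reply is that the tables do count HFA-134a reactions. Each HFA-134a period has 15 doses, and any event from Day 1 of that period is a TEAE under HFA-134a. Cough, throat irritation or taste complaints may well recur, and with full recurrence the imbalance is nil. This stands. A reader might infer that reactions are counted against HFA-152a only. The documents do not support that for reactions in general; it is limited to those that occur once and do not return.

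A reader might also assume two identical propellants, with reactions only at the first inhalation ever, and conclude that the whole excess falls on HFA-152a. That does not follow. If the propellants are interchangeable in this respect, the training inhalation uses up the reaction and the expected count is 0 against 0. The imbalance needs reactions specific to each propellant. Nor can a first lifetime exposure be placed at training: earlier HFA-134a use is not documented, and the propellant, if any, of the separate AIM placebo inhaler (Protocol 6.1.2.4.1) is not stated.

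A third tempting inference is that training selects subjects who tolerate HFA-134a. The stated criterion is correct use of an inhaler that functions like the study device. That is technique, and it bears on both treatments alike.

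Reactions may also be rare. In the first-in-human study described in Protocol 1.1, 8 volunteers took 4 puffs of HFA-152a with no adverse events. This is reassuring but weak: at a true rate of 10%, the chance of none in 8 is 0.9^8 = 0.43.

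Finally, the adverse event output is descriptive, the study is called exploratory, and for randomised subjects every pre-treatment event is listed with onset day and duration. With 20 subjects a careful reader can find them. This lowers the stakes. It does not help with screening failures, who are in neither the eCRF nor the Randomised Set, although serious events would still be reported under Protocol 10.9.

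**Conclusion.** The point holds in a limited form. By the plan's own definitions, and apart from the incomplete-date and delayed-onset cases above, a reaction at the first in-study exposure to HFA-134a cannot enter the TEAE or ADR tables. One at the first exposure to HFA-152a enters the TEAE tables, and the ADR tables if related or with relationship missing. A non-serious reaction in a subject who then fails screening leaves no trace in the study database.

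The possible bias is against HFA-152a or nil, and it comes only from propellant-specific reactions that do not recur on re-exposure. Its size cannot be derived from the documents. The illustration at an assumed 10% rate gives a spurious difference of between 0 and 2.0 subjects in 20, depending wholly on assumed recurrence. The matter concerns the descriptive safety tables and has no bearing on the MCC analysis.

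**What to change.** In SAP 3.1.2, flag adverse events that start on the day of the HFA-134a training, after the training inhalations. In SAP 3.1.3, add one supplementary table of these events (overall, related, and by SOC and preferred term) next to the events on Day 1 of each period, by propellant. Keep it separate from the HFA-134a TEAE column. Merging in the whole 3- to 22-day screening interval would add background events to one propellant with no counterpart for the other. Later pre-dose events stay in the listing as now.

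Reconcile Protocol 11 with Protocol 10.8, so that adverse events after training are entered in the eCRF for training and screening failures too.

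The cost is SAP wording, one descriptive table and a few eCRF entries. Adverse event start times and training data are already collected (SAP 3.1.1 and 4.6.1), but the documents do not say that the clock time of the training inhalations is recorded, so that may need adding. The training-day exposure is not randomised, and Day 1 includes an evening dose as well as the morning one, so the table supports a side-by-side reading and not a formal comparison.
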